## **Randomization:**

The proposed study will use a two-group randomized design with 3 assessment points (baseline, approximately 11 weeks, and approximately 19 weeks). Following baseline assessments, the participant will be randomly assigned to one of the two study groups (Intervention or Usual Care). The Pocock-Simon covariate adaptive randomization procedure will be used so that there will be approximately equal number of subjects assigned to the two groups within each covariate level (depressed or not and high or low ADL) and within each study site. The statistician will develop the randomization scheme and share it with the project coordinator and a research staff member at each site. When a caregiver is enrolled in the study, this staff member at site will obtain the group assignment for that caregiver from the randomization system.

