The post-test assessments (stroke caregivers' depression, perceived stress, knowledge, burden, perception of positive aspects of caregiving, self-efficacy, health-related quality of life (HRQOL), and satisfaction with care) will be collected at approximately 11 weeks and approximately 19 weeks after the Veterans' discharge. A study team member at the main study site (Gainesville), who will be blinded to the group assignment of the caregivers, will telephone the caregivers to obtain the post-test assessments. The research staff will also review the Veterans' CPRS record and document the Veterans' healthcare utilization since their discharge to home. To minimize loss to follow-up, we will contact participants 24 hours before each post-test assessment to remind them of their scheduled appointment time. We will also mail postcards to enrolled caregivers who we cannot contact after 3 attempts to reduce attrition.

In the event that the RN conducting the intervention or the research personnel conducting the pre-and posttest assessments uncovers that the caregivers are experiencing unmanageable stress, but not severe stress, the research personnel will advise the caregivers to call their assigned VA primary care social workers and primary care clinicians (MD, ARNP, PA) of their Veterans' care team. The research personnel will also give the caregivers the phone number of the VA Caregiver Support Line and other referral sources as needed. If the research personnel assesses that the caregivers are in severe stress or crisis or if the research personnel uncovers that the Veteran has serious changes in his/her health, the research personnel will call the primary care provider/social worker of the Veteran's care team or the local emergency response system (9-1-1). In the event that any abuse or neglect is suspected, study personnel will follow established procedures by oversight agencies, including VHA as directed in the VA Handbook 1050.01, to contact the Office of Inspector General, Office of Investigation, as well as the IRB and the state of Florida Abuse Hotline.

Efforts to improve retention of participants: To improve the chances that participants will complete the project, we will conduct the 11-week and 19-week post-test assessments at times that are convenient to the caregivers.

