The website includes the following sections: 1) an extensive list of resources; 2) a library of the monthly/bimonthly patient education newsletters; 3) self-help tools; 4) a glossary of medical terms with phonetic pronunciations; 5) testimonials or stories from stroke caregivers; 6) links to other stroke and caregiver websites; 7) a factsheet library; 8) a problem-solving training module, and 9) a problem-solving diary form. A major component of our proposed intervention is the comprehensive library of factsheets for stroke caregivers (see following table for categories and topics).

b) Intervention Component (#1): Transition-to-Home Telephone Session: (includes the RESCUE problem-solving module and diary accessible on http://www.cidrr8.research.va.gov/rescue/ and in appendix). The research nurses at each site will conduct telephone sessions with the caregivers shortly after baseline data is collected. The nurses will follow a structured protocol (see following table) and script. The problem-solving module on the RESCUE website serves as the primary teaching tool for this session. Similar to how teachers use power-point presentations for classroom instruction, the nurses will use the module to teach the problem solving method.

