We will maintain records of "exact correspondence" of the caregiver and nurse communications on the messaging center. We will also collect data on the time spent or minutes that the caregivers and study nurse interact via the messaging center. This data will allow us to monitor participant adherence. To minimize loss to follow-up, if necessary, we will contact participants 24 hours before scheduled data collections/sessions to remind them of their session. We will also mail reminder postcards to enrolled caregivers that we are unable to contact after 3 attempts to reduce attrition.

If after starting, a caregiver is unable or unwilling to continue with the intervention they will be offered the opportunity to discontinue the intervention but remain in the study for data collection phone calls. These phone calls will occur approximately 11 and 19 weeks after baseline data collection. To be eligible to complete these optional data collection phone calls, the caregiver must have completed at least one phone or messaging center intervention session.

Usual Care Group: The caregivers' Veterans will receive usual or standard care. The caregivers will receive the standard information and discharge planning that is provided to all stroke caregivers. There will be no changes in the care the Veterans normally receive or in the information and discharge planning that the caregivers normally receive.

**Fidelity Considerations:** We will develop standardized manuals and protocols. This manual will provide step-by-step guidelines on recruiting/enrolling participants, implementing the informed consent process, in conducting the transition-to-home and in-home sessions and implementing the data collection procedures. We will provide extensive training to all of our team members. The PI and one staff member will periodically visit (minimally once a year) the Tampa and Miami study sites and observe the research nurses conducting the transition-to-home session. Feedback will be provided as needed.

Similar to our previous projects, we will have regular conference calls with our team members at the three study sites (Gainesville, Miami and Tampa). In these meetings, team members will describe how they are

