## **Data Analysis:**

Hypothesis #1 (primary): Stroke caregivers who receive the intervention will have less depressive symptoms at approximately 11 and 19 weeks compared to stroke caregivers in the usual care group. Our primary endpoint is the caregiver depressive score. The focus of the primary analysis will be to examine the effect of the intervention based on "intention to treat." Data from all the participants will be part of the primary analyses regardless of actual number of completed in-home sessions. Thus, we are examining the effectiveness of the intervention taking into account real world compliance factors. As an exploratory study element, we will assess compliance and attempt to determine its effect on study results.

For the primary analysis, the general linear mixed model for repeated measures will be used to model the follow-up depression times (approximately 11 and 19 weeks after baseline data collection), adjusted for site and baseline scores as fixed effects. Since the Tampa site has a standardized, discharge planning process that involves Veteran education while the other sites have no discharge planning process, there may be different responses due to usual care between the Tampa versus other sites. Thus, we will first explore whether or not there is a differential treatment effect at the Tampa site by fitting a full model that allows for Tampa to have a differential time and group effect for each time point. Let  $y_{ij}$  be the depression score for person i at time j, then Full fixed effects model will be:

$$E(y_{ij}) = \beta_0 + \beta_1 Baseline_i + \beta_2 Tampa_i + \Sigma_s \beta_{3s} I(Site_i = s) + \beta_4 Time_{ij} + \beta_5 Group_i + \beta_6 Group_i *Time_{ij} + \beta_7 Tampa_i *Time_{ij} + \beta_8 Tampa_i *Group_i + \beta_9 Tampa_i *Group_i *Time_{ij}$$

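### Intervention caregivers who discontinue with no completed session are not eligible for the 11- and 19-week calls, so the primary outcome is withheld by rule in one arm, contrary to intention to treat

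*Combined protocol and SAP*

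**What the plan says.** The rule stands in section 6, Research Plan, under Intervention Component (#2), just before the Usual Care Group paragraph. The offer reads: "If after starting, a caregiver is unable or unwilling to continue with the intervention they will be offered the opportunity to discontinue the intervention" while staying in the study for the 11- and 19-week data collection calls. It is then limited: to be eligible for these calls, which are called optional, "the caregiver must have completed at least one phone or messaging center intervention session".

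Four other places bear on it:

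- **Randomization:** assignment to a group follows the baseline assessments.
- **Intervention Component (#1):** the research nurses "at each site will conduct telephone sessions with the caregivers shortly after baseline data is collected". The first session therefore comes after randomization or close to it, and nothing makes it a condition of being randomized.
- **Data Collection:** a blinded team member "will telephone the caregivers to obtain the post-test assessments", which include the depression score. No session condition is attached.
- **Data Analysis, Hypothesis #1:** the primary analysis is by intention to treat, and "Data from all the participants will be part of the primary analyses regardless of actual number of completed in-home sessions". For that analysis, "the general linear mixed model for repeated measures will be used to model the follow-up depression times", with baseline score and site as fixed effects.

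**The concern.** A caregiver can be randomized to the intervention and stop before completing any session. Under the discontinuation rule that caregiver does not qualify for the calls that yield the primary endpoint, and no other paragraph expressly provides follow-up after stopping. A usual care caregiver cannot fail the condition, because that arm has no sessions. The rule is therefore a follow-up criterion that depends on behaviour after randomization, in one arm.

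The primary model has only the 11- and 19-week scores as responses, and baseline is a covariate. A caregiver with neither score adds nothing to the treatment estimate. In effect the model treats the missing intervention caregivers as if they would have scored like starters with the same baseline and site. That is wrong in two situations:

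- non-starters differ in prognosis beyond baseline score and site; or
- the intervention helps those who start and does nothing for those who do not.

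In the second situation the intention-to-treat effect is overstated even when prognosis is equal.

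**Working it through.** **The plan's own figures** (Rationale for Study Sample Size): SD 8.2, difference 3.5, 84 evaluable per group, 5% significance level (two-sided assumed), 30% dropout.

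- Standard error of the difference: 8.2 × √(2/84) = 1.265.
- Power: Φ(3.5/1.265 − 1.96) = 79.0%, against the stated 80%.
- Enrolment: 84/(1 − 0.30) = 120 per group, as stated.

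The stated design is therefore a fair basis for judging the size of the bias.

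**Assumed inputs.** The documents give neither of these:

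- p: the share of the intervention arm that stops with no completed session.
- Δ: how many CES-D points worse these caregivers would score than starters, given baseline and site. Higher CES-D is worse.

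Other dropout is taken as unrelated to outcome, and 84 per arm is held fixed.

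**Case 1: no treatment effect, prognosis differs.** Let m be the starters' mean. The full-arm mean is (1 − p)m + p(m + Δ) = m + pΔ. The analysis sees only m, so the bias is b = pΔ, in favour of the intervention when Δ > 0. The two-sided false-positive rate is Φ(b/1.265 − 1.96) + Φ(−b/1.265 − 1.96).

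| p | Caregivers of 120 | Δ | Bias b | False-positive rate |
|---|---|---|---|---|
| 5% | 6 | 2 | 0.1 | 5.1% |
| 10% | 12 | 4 | 0.4 | 6.2% |
| 15% | 18 | 6 | 0.9 | 11.0% |
| any | – | 0 | 0 | 5.0% |
| 10% | 12 | −2 | −0.2 (against the intervention) | 5.3% |

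**Case 2: equal prognosis, only starters benefit.** Suppose starters gain 3.5 points and non-starters nothing. The intention-to-treat effect is (1 − p) × 3.5, while the model estimates 3.5, so the overstatement is p × 3.5.

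| p | Intention-to-treat effect | Model estimate | Overstatement |
|---|---|---|---|
| 5% | 3.33 | 3.5 | 0.18 |
| 10% | 3.15 | 3.5 | 0.35 |
| 15% | 2.98 | 3.5 | 0.53 |

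In this case power at 84 per group for the true intention-to-treat effect is 74.8%, 70.2% or 65.2%, not 79.0%.

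**The case against.** **The scope is narrow.** The offer opens with caregivers who have already started, one telephone session is enough to qualify, and Data Collection sets the routine calls with no session condition. This stands as a limit. A caregiver who completes nothing but never formally stops is not expressly refused, and the two paragraphs leave that case unclear. The opening clause does not rescue the rule, however: those who never start are outside the offer, and those who start but complete nothing fail the condition.

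**The intention-to-treat sentence mentions in-home sessions only.** This is true, and a caregiver with the telephone session and no in-home session stays eligible, so that clause is honoured. The conflict is confined to caregivers with no session of either kind. The preceding sentence states intention to treat without qualification, and the data are to come from all participants.

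**Handling of Missing Data already covers dropout.** It says the mechanism will be explored, and that unspecified techniques will be used if missing at random is implausible. It cannot recover outcomes that the rule leaves uncollected.

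**The size is all assumption, and not all of it is due to the rule.** This largely stands. The 15% and 6-point row is an extreme corner. The sample size section calls 3.5 the mean intervention effect, so assigning it to starters only is a scenario. Non-starters might also answer less often if called. If they responded half as often at p = 10% and Δ = 4, they would be 0.05/0.95 = 5.3% of respondents; calling them would remove 0.053 × 4 = 0.21 of the 0.40 points and leave 0.19. The tabulated biases are therefore upper bounds, for each p and Δ, on what the rule causes.

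**Conclusion.** The concern holds. For intervention caregivers who discontinue with no completed session, the plan makes collection of the primary outcome depend on adherence, in one arm, against its own analysis principle. The text alone establishes this.

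The size cannot be found from the documents. Over the assumed range of 5% to 15% non-starters, the null-effect bias runs from 0.1 to 0.9 points when non-starters do worse. It is zero when they do not differ and reversed when caregivers decline because they feel little need. The direction is likely, but not proven, to favour the intervention. If only starters benefit, the overstatement is 0.18 to 0.53 points with no prognostic difference needed. The affected group may be small, but the rule has no stated rationale and outcomes not collected on time cannot be recovered, so it should be changed.

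**What to change.** 1. In the discontinuation paragraph under Intervention Component (#2), delete the one-session condition and the wording that restricts the offer to caregivers who have already started.
2. State there and in Data Collection that the 11- and 19-week calls are offered to every randomized caregiver, whatever number of sessions was completed, unless consent has been withdrawn or participation has ended because the Veteran died (Eligibility Criteria).
3. State in Data Analysis that all scores so collected enter the primary model.
4. Optionally, prespecify a delta-adjusted sensitivity analysis by arm for caregivers who still have no outcome. This would make specific the general commitment in Handling of Missing Data.

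**Cost.** Protocol wording, and two more assessment calls per affected caregiver: 2 × 120 × p = 12, 24 or 36 at p = 5%, 10% or 15%. The 24-hour reminder before each assessment, and postcards after three failed attempts, add a little. Existing staff can absorb this. The optional analysis is one more model run.

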## **Data Analysis:**

Hypothesis #1 (primary): Stroke caregivers who receive the intervention will have less depressive symptoms at approximately 11 and 19 weeks compared to stroke caregivers in the usual care group. Our primary endpoint is the caregiver depressive score. The focus of the primary analysis will be to examine the effect of the intervention based on "intention to treat." Data from all the participants will be part of the primary analyses regardless of actual number of completed in-home sessions. Thus, we are examining the effectiveness of the intervention taking into account real world compliance factors. As an exploratory study element, we will assess compliance and attempt to determine its effect on study results.

For the primary analysis, the general linear mixed model for repeated measures will be used to model the follow-up depression times (approximately 11 and 19 weeks after baseline data collection), adjusted for site and baseline scores as fixed effects. Since the Tampa site has a standardized, discharge planning process that involves Veteran education while the other sites have no discharge planning process, there may be different responses due to usual care between the Tampa versus other sites. Thus, we will first explore whether or not there is a differential treatment effect at the Tampa site by fitting a full model that allows for Tampa to have a differential time and group effect for each time point. Let  $y_{ij}$  be the depression score for person i at time j, then Full fixed effects model will be:

$$E(y_{ij}) = \beta_0 + \beta_1 Baseline_i + \beta_2 Tampa_i + \Sigma_s \beta_{3s} I(Site_i = s) + \beta_4 Time_{ij} + \beta_5 Group_i + \beta_6 Group_i *Time_{ij} + \beta_7 Tampa_i *Time_{ij} + \beta_8 Tampa_i *Group_i + \beta_9 Tampa_i *Group_i *Time_{ij}$$

with covariates for baseline depression and time since discharge (*Baseline*), site (e.g., *Tampa*=1 if Tampa, 0 otherwise; and  $\beta_{3s}$  represent effects of sites compared to reference site Gainesville), time (*Time*=0 for 11 weeks, 1 for 19 weeks), and group (0 if active control, 1 if intervention). Of primary interest is the estimated within-site intervention effect at approximately 11 weeks after baseline data collection, controlling for baseline and stratifying by site. The initial test will be the test of  $\beta_8$ +  $\beta_9$ =0, which tests whether the Tampa site has a differential group effect compared to the other sites at approximately 11 weeks after baseline data collection. If a site difference in treatment effect is found, then results will be conditional on Tampa or Miami/Gainesville. In this case, the primary tests of interest will be the estimated within-site intervention effect at approximately 11 weeks after baseline data collection, controlling for baseline and stratifying by site. In the model above, this corresponds to the test of  $\beta_5$  =0 for other sites and  $\beta_5$  + $\beta_8$ =0 for Tampa. If no difference is found in our initial interaction test, we will assume that the Tampa site does not have a differential treatment effect and the interaction will be removed from the model. The new fixed effect portion of the model will simplify to the Reduced model:

$$E(y_{ij}) = \beta_0 + \beta_1 Baseline_i + \beta_2 Tampa_i + \Sigma_s \beta_{3s} I(Site_i = s) + \beta_4 Time_{ij} + \beta_5 Group_i + \beta_6 Group_i *Time_{ij}$$

Of primary interest is the estimated within-site intervention effect at approximately 11 weeks after baseline data collection, controlling for baseline covariates and stratifying by site. In the model above, this is the test of  $\beta_5$  =0. In order to control for possible chance sample imbalances resulting from randomization, the model will include covariates for baseline prognostic factors (e.g., discharge from hospital, community living center, or rehabilitation facility; caregivers' relationship to Veteran; number of previous strokes among Veterans, etc.), deemed to have significant relationships with response and groupwise imbalances. Thus, analyses will be able to compare the groups on the measure of interest while controlling for these factors. As a supplemental analysis we will assess long term intervention effects at the approximately 19 week after baseline data collection time point. In the Full model above, this is the test of  $\beta_6$  =0 for other sites, and  $\beta_6$ +  $\beta_9$ =0 for Tampa. In the reduced model, this is simply the test of  $\beta_6$  =0. All tests will be performed at the  $\alpha$ =0.05 significance level. The correlation among observations from the same person will be accounted for through the inclusion of a random person effect into the mixed model analysis.

Hypotheses #2 (secondary): (2a) Stroke caregivers who receive the intervention will have superior outcomes (i.e., less burden, less stress, greater self-efficacy, perceive greater positive aspects of

caregiving, better HRQOL, and greater satisfaction with care) at approximately 11 and 19 weeks after baseline data collection than caregivers in the usual care group.

The analysis plan for Hypothesis 2 will closely follow the plan outlined above for Hypothesis 1 for each secondary outcome of interest.

Hypotheses #3 (secondary): Veterans whose caregivers receive the intervention will have better functional abilities at approximately 11 and 19 weeks after baseline data collection and less healthcare utilization at approximately 11 and 19 weeks after baseline data collection compared to Veterans whose caregivers are in the usual care group.

Since the Barthel Index score can be treated as continuous, the analysis plan follows exactly as above in Hypothesis 1. Since the Veteran healthcare utilization measures are count data, the models will be somewhat different. There will be no baseline covariates added to the model, as they are not applicable to the count measures. Analyses will be conducted for the period following baseline data collection to approximately 11 weeks and 19 weeks after baseline data collection. Generalized linear models for count data (such as Poisson or negative binomial regression models, depending on the presence or absence of over-dispersion) will be employed to determine the group effects on healthcare utilization. As before, the site type will be included in the full model and possible site differences will be accounted for. Log link functions will be employed on the count data to create the correct distributional data forms. As before, in order to control for possible sample imbalances resulting from randomization, all models will include covariates for prognostic factors deemed to have significant relationships with response and significant groupwise imbalances. Thus, analyses will be able to compare the groups on the measures of interest while controlling for these factors.

Handling of Missing Data: We should not have a problem with missing data as our data will be collected inperson or over the telephone. Our data collectors will receive extensive training on interviewing and how to politely encourage participants to answer all questions on research instruments. In the event of drop-outs, the missingness mechanism will be explored. If the assumption of Missing Completely at Random (MCAR) or the common assumption of Missing at Random (MAR) are plausible, then little change to the analysis plan is necessary. The mixed models analysis using direct-likelihood approaches will be unbiased and appropriate. Study efficiency (power) will of course be affected by the smaller amount of available information, thus we have inflated the planned recruitment sample size. If the missingness assumptions are not plausible, then Missing Not at Random (MNAR) techniques will be employed and analysis results will be interpreted with caution.

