Rationale for Study Sample Size: The sample will consist of 240 caregivers. Assuming a standard deviation of 8.2, 84 subjects per group would achieve 80% power to detect a mean intervention effect size of 3.5 on depression at a 5% significance level. The sample size of 120 per group (i.e., intervention group, usual care group) was selected to account for the occurrence of a (30%) dropout rate. The 30% drop-out rate is a conservative estimate of attrition and is based on previous caregiver problem-solving intervention studies in the literature and on the attrition rates found in the internet intervention studies of our consultants, Drs. [name] and [name]. The expected effect size and variability was deemed reasonable based on a number of sources. In a study of caregivers of Alzheimer's patients, the investigative team described large changes pre- and post-treatment in a clinical setting, with depression from time of admission to 4 weeks post decreasing 20 points for "recovered" patients and 12 points for "still ill" patients. In a study of a telephone intervention to family caregivers of stroke caregivers, found an estimated 1 month treatment effect of 3.1.

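### The Tampa test that chooses the form of the 11-week primary analysis is labelled 11-week but is algebraically the 19-week contrast, and correcting only the symbol would raise the false-claim rate

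*Combined protocol and SAP*

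**What the plan says.** All of this is in the Combined protocol and SAP, Data Analysis, Hypothesis #1, unless noted.

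- **Reason for the step.** Tampa has a standardized discharge planning process, so "there may be different responses due to usual care between the Tampa versus other sites".
- **Model.** In the full model β5 belongs to Group, β6 to Group×Time, β8 to Tampa×Group and β9 to Tampa×Group×Time. Time is coded "0 for 11 weeks, 1 for 19 weeks".
- **Gate.** The first test is β8+β9=0, "which tests whether the Tampa site has a differential group effect compared to the other sites at approximately 11 weeks after baseline data collection".
- **Gate significant.** "In this case, the primary tests of interest will be the estimated within-site intervention effect at approximately 11 weeks", given as β5=0 for the other sites and β5+β8=0 for Tampa.
- **Gate not significant.** "If no difference is found in our initial interaction test, we will assume that the Tampa site does not have a differential treatment effect"; the interaction is dropped and the primary test is β5=0 in the reduced model.
- **Level.** "All tests will be performed at the" 0.05 level. No allowance is made for the gate or for the second primary test.
- **Sample size** (Rationale for Study Sample Size). With an SD of 8.2, "84 subjects per group would achieve 80% power to detect a mean intervention effect size of 3.5". This is one two-group comparison on 2 × 84 = 168 completers.

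**The concern.** The primary time point is 11 weeks, and the 19-week comparison is called supplemental. If the gate is really the 19-week contrast, a supplemental visit decides how the primary result is obtained. The 11-week analysis could be split because of a Tampa difference seen only at 19 weeks, or pooled despite one seen at 11 weeks. The formula and its description cannot both be followed.

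The obvious edit is to delete β9. But the gate would then use the same 11-week data as the two subgroup tests it opens, each at 0.05, so the edit could do harm. The plan also treats a non-significant gate as grounds to assume that Tampa does not differ, which is safe only if the gate has reasonable power.

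**Working it through.** **1. Algebra of the gate (no assumptions).** The group effect implied by the full model is:

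| | Other sites | Tampa | Tampa minus others |
|---|---|---|---|
| Time=0 (11 weeks) | β5 | β5+β8 | β8 |
| Time=1 (19 weeks) | β5+β6 | β5+β6+β8+β9 | β8+β9 |

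So β8+β9 is the 19-week contrast. The plan's own 11-week follow-on tests, β5 and β5+β8, differ by β8, which confirms it. Reversing the time coding does not help, because those follow-on tests would then be 19-week contrasts.

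**2. The plan's power figure.** SE = 8.2 × √(2/84) = 1.265 and 3.5/1.265 = 2.77. Two-sided 5% power is Φ(2.77 − 1.96) = 79%, close to the stated 80%. Also 84/0.7 = 120 per group, as planned.

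**3. Inputs the documents do not give (assumed).** Tampa share f = 1/8, 1/5, 1/3. Correlation ρ between the 11- and 19-week Tampa contrasts = 0.3, 0.5, 0.7, 0.85. Tests are taken as two-sided, with complete data on 168 and 1:1 allocation within site.

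**4. False primary claims with no effect anywhere.** The Tampa and other-site 11-week estimates are independent normal, with variances 2/(84f) and 2/(84(1−f)) in SD units. If the gate has |z|>1.96, a claim is made when either subgroup has |z|>1.96; otherwise when the pooled estimate does. Simulation with millions of draws per setting gives:

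| Procedure | Chance of at least one false primary claim |
|---|---|
| As written (19-week gate), ρ = 0.3 / 0.5 / 0.7 / 0.85 | 5.5% / 5.9% / 6.5% / 7.2–7.3% |
| Gate corrected to β8, f = 1/8 / 1/5 / 1/3 | 8.6% / 8.3% / 8.1% |
| Pooled test alone | 5.0% |

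The rise has a simple cause. When the β8 gate fires by chance, at least one subgroup test is significant 67% to 76% of the time; for the 19-week gate at ρ = 0.5 this is about 22%. Per-visit regressions with eight site effects, a baseline covariate and t critical values agree (ρ 0.3 to 0.7): 5.4% to 6.6% as written and 7.9% to 8.7% corrected. Testing each subgroup at 0.025 does not cure it: with the β8 gate the rate is still 6.9% to 7.2%.

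**5. How often the formula splits on the wrong week.** With no site difference the gate fires in 5% of trials. Among those splits, the 11-week Tampa contrast is itself not significant in 90%, 82%, 67% and 49% at ρ = 0.3, 0.5, 0.7 and 0.85. For ρ = 0.3 and 0.85 that is 4.5% and about 2.5% of all trials. A Tampa difference present only at 11 weeks would trigger the printed gate 5% of the time, its false-positive rate.

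**6. Power of a gate on the right week, for a 3.5-point Tampa difference.** SE = SD × √(2/(84f) + 2/(84(1−f))).

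| f | SE at SD 8.2 | Power, SD 8.2 | Power, SD 7.10 (baseline r = 0.5) | Power, SD 5.86 (r = 0.7) |
|---|---|---|---|---|
| 1/8 | 3.83 | 15% | 18% | 25% |
| 1/5 | 3.16 | 20% | 25% | 34% |
| 1/3 | 2.68 | 26% | 33% | 45% |

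The adjusted SD is 8.2 × √(1 − r²), with r assumed.

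**7. Power after a split, 3.5 points, SD 8.2.** Tampa: SE = 8.2 × √(2/10.5) = 3.58 at f = 1/8, power 16%; 8.2 × √(2/28) = 2.19 at f = 1/3, power 36%. Other sites: SE = 1.35 and 1.55, power 73% and 62%. Pooled: 79%. Adjusting for baseline raises all of these; at r = 0.5 Tampa has 20% to 45%, the other sites 85% to 74%, and the pooled test 89%.

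**The case against.** The algebra is not in dispute; the case on the other side is about weight.

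- **The intended week can be recovered, and the two gates seldom change the outcome.** Text and follow-on tests name 11 weeks throughout. Under the same assumptions, with no site difference, the two gates disagree in 5% to 9% of trials. Whether any primary claim is made differs in 1.8% to 3.4% of trials with no effect, and in about 0.7% to 1.4% with 3.5 points at every site. These figures stand. They do not count which site the claim is for, and a primary analysis should not depend on which half of a sentence the analyst follows.
- **The wrong-week case may be unlikely.** Tampa's discharge process is a standing feature, so a difference may persist. If it persists in full to 19 weeks, the printed gate has the same power as the corrected one. That is fair, but that power is still only 15% to 26% unadjusted.
- **The error-rate excess is modest and two-directional.** The plan promises no familywise rate. False claims of benefit alone are 2.7% to 3.7% as written and 4.1% to 4.3% with β8, against 2.5% pooled. This stands: the contradiction carries the point, and the error rate matters mainly as a warning against the one-symbol edit.
- **A single pooled test replaces a choice the plan explains.** This is a real cost, stated below.

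**Conclusion.** The concern holds. The contradiction between the gate's formula and its label is exact, rests on no assumption, and sits in the step that selects the primary analysis, so it must be resolved before the analysis is run. Correcting the symbol alone raises the chance of a false primary claim from 5.5–7.3% to 8.1–8.6%. These sizes depend on the assumed Tampa share and visit correlation, but the direction was the same in every setting tried. A non-significant gate does not justify assuming that Tampa is the same: unadjusted power for 3.5 points is at most 26%, and at most 45% with a baseline correlation of 0.7.

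**What to change.** In Data Analysis, Hypothesis #1:

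1. State that the single primary test is β5=0 in the reduced model (pooled, site-adjusted, 11 weeks) at two-sided 5%, whatever the Tampa contrast shows. Describe it as the average effect across sites, so that it does not rely on Tampa being the same.
2. Report the Tampa-by-group contrast from the full model as a pre-specified secondary heterogeneity analysis: β8 at 11 weeks and β8+β9 at 19 weeks, with Tampa and other-site estimates and confidence intervals. Remove the sentence that assumes no difference after a non-significant test.
3. Change the reference to Miami/Gainesville to all other sites, which is what the model codes.
4. While editing, check the supplemental 19-week tests against the same coding: β6 is the change in effect from 11 to 19 weeks, whereas the 19-week effect at the other sites is β5+β6.

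Carry the wording over to Hypothesis #2 and the Barthel Index, whose analyses follow Hypothesis #1. The change is to SAP wording only and keeps the comparison the trial was sized for. Its cost is that a Tampa-specific estimate can no longer be a primary result, although the plan gives a sensible reason for asking about Tampa.
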